6.6.1. Blood Samples

- Blood sample collection for the following laboratory analyses will be performed at every visit, unless specified:
 - Serum pregnancy test (females of childbearing potential only). If the test is positive, the subject will not be randomized (**Screening and Days 29, 57, 85, 113, 141, 169, 197 and 225**)
 - Serum FSH test (required for female subjects who have stopped menstruating for ≥ 12 months but do not have documentation of ovarian hormonal failure) (**Screening only**)
 - Urine pregnancy test (females of childbearing potential only). If the test is positive, confirmatory serum test should be sent and study drug dosing should be delayed until results obtained (**Day 1**)
 - Chemistry profile: alkaline phosphatase, AST, ALT, GGT, total bilirubin, direct and indirect bilirubin, total protein, albumin, LDH, CPK, bicarbonate, BUN, calcium, chloride, creatinine, glucose, phosphorus, magnesium, potassium, sodium, uric acid, amylase (reflex lipase testing is performed in subjects with total amylase $> 1.5 \times \text{ULN}$) (**All visits except Days 2, 4, 8 and 9**). Subjects will be required to fast overnight (≥ 6 hours) prior to visit on Days 3, 7, 10, 85, 169 and 225.
 - Estimated glomerular filtration rate according to the Cockcroft-Gault formula for Creatinine clearance (**All visits except Days 2, 4, 8 and 9**)
Male:
$$\frac{(140 - \text{age in years}) \times (\text{wt in kg})}{72 \times (\text{serum creatinine in mg/dL})} = \text{CLcr (mL/min)}$$

Female:
$$\frac{(140 - \text{age in years}) \times (\text{wt in kg}) \times 0.85}{72 \times (\text{serum creatinine in mg/dL})} = \text{CLcr (mL/min)}$$
 - Hematology profile: complete blood count (CBC) with differential and platelet count (**All visits except Days 2, 4, 8 and 9**)
 - CD4+ cell count (**Screening and Days 1, 10, 29, 43, 57, 85, 113, 141, 169, 197 and 225**)
 - Plasma HIV-1 RNA. Any subsequent HIV-1 genotype and phenotype testing will be performed as described in Section 6.7.
 - HIV-1 genotype and phenotype for PR, RT, IN, and capsid (**Screening only**)
 - HIV-1 capsid genotype and phenotype (**Day 10**)
 - HIV DNA genotyping (**Days 85, 169 and 225**)

- Hepatitis B virus (HBV) serologies (HBV surface antigen, HBV core antibody, HBV surface antibody) (**Screening only**)
- Hepatitis C virus (HCVAb) serology (**Screening only**)

CCU [REDACTED]

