6.6.2. Urine Samples

Urine samples will be collected for the following laboratory analyses at every study visit, unless otherwise specified:

- Urinalysis and urine Chemistry: including color & clarity, specific gravity, pH, glucose, ketones, bilirubin, urobilinogen, blood, nitrite, leukocyte esterase and microscopic (if microscopic elements are seen), urine protein, albumin, creatinine, phosphate, calcium, magnesium and uric acid (**All visits except Days 2, 4, 8 and 9**)
- Urine pregnancy test (females of childbearing potential only). If the test is positive, confirmatory serum test should be sent and study drug dosing should be delayed until results obtained (**Day 1**)
- Urine storage (**All visits except Screening, Days 2, 4, 8 and 9**)

CCI

CCI

6.7. Management of Virologic Failure after Initiation of B/F/TAF on Day 10

Subjects who experience either suboptimal virologic response (SVR) or virologic rebound (VR) after initiating B/F/TAF, as defined below, will be considered to have virologic failure.

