Alkaline Phosphatase	1.25 to 2.50 × ULN	> 2.50 to 5.00 × ULN	> 5.00 to 10.00 × ULN	> 10.00 × ULN
Total Amylase	> 1.0 to 1.5 × ULN	> 1.5 to 2.0 × ULN	> 2.0 to 5.0 × ULN	> 5.0 × ULN
Pancreatic Amylase	> 1.0 to 1.5 × ULN	> 1.5 to 2.0 × ULN	> 2.0 to 5.0 × ULN	> 5.0 × ULN
Lipase	> 1.0 to 1.5 × ULN	> 1.5 to 3.0 × ULN	> 3.0 to 5.0 × ULN	> 5.0 × ULN
Albumin Pediatrics <16 years	-	2.0 to < LLN g/dL 20 to < LLN g/L	< 2.0 g/dL < 20 g/L	NA
≥ 16 years	3.0 g/dL to < LLN 30 g/L to < LLN	2.0 to < 3.0 g/dL 20 to < 30 g/L	< 2.0 g/dL < 20 g/L	NA

URINALYSIS				
	Grade 1	Grade 2	Grade 3	Grade 4
Hematuria (Dipstick)	1+	2+	3-4+	NA
Hematuria (Quantitative) See Note below				
Females	>ULN - 10 RBC/HPF	> 10-75 RBC/HPF	> 75 RBC/HPF	NA
Males	6-10 RBC/HPF	> 10-75 RBC/HPF	> 75 RBC/HPF	NA
Proteinuria (Dipstick)	1+	2-3+	4+	NA
Proteinuria, 24 Hour Collection				
Adult and Pediatric ≥ 10 Years	200 to 999 mg/24 h	>999 to 1999 mg/24 h	>1999 to 3500 mg/24 h	> 3500 mg/24 h
Pediatric > 3 Mo to < 10 Years	201 to 499 mg/m ² /24 h	>499 to 799 mg/m ² /24 h	>799 to 1000 mg/m ² /24 h	> 1000 mg/ m ² /24 h
Glycosuria (Dipstick)	1+	2-3+	4+	NA

Notes:

- Toxicity grades for Quantitative and Dipstick Hematuria will be assigned by Covance Laboratory, however for other laboratories, toxicity grades will only be assigned to Dipstick Hematuria.
- With the exception of lipid tests, any graded laboratory test with a result that is between the LLN and ULN should be assigned Grade 0.
- If the severity of a clinical AE could fall under either one of two grades (eg., the severity of an AE could be either Grade 2 or Grade 3), select the higher of the two grades for the AE.

CARDIOVASCULAR				
	Grade 1	Grade 2	Grade 3	Grade 4
Cardiac Arrhythmia (general) (By ECG or physical exam)	Asymptomatic AND No intervention indicated	Asymptomatic AND Non-urgent medical intervention indicated	Symptomatic, non-life-threatening AND Non-urgent medical intervention indicated	Life-threatening arrhythmia OR Urgent intervention indicated
Cardiac-ischemia/Infarction	NA	NA	Symptomatic ischemia (stable angina) OR Testing consistent with ischemia	Unstable angina OR Acute myocardial infarction
Hemorrhage (significant acute blood loss)	NA	Symptomatic AND No transfusion indicated	Symptomatic AND Transfusion of ≤ 2 units packed RBCs (for children ≤ 10 cc/kg) indicated	Life-threatening hypotension OR Transfusion of > 2 units packed RBCs indicated (for children ≤ 10 cc/kg) indicated

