#### **7.2.2.1. Treatment-Emergent Laboratory Abnormalities**

Treatment-emergent laboratory abnormalities are defined as values that increase at least 1 toxicity grade from baseline at any postbaseline visit. If the relevant baseline laboratory value is missing, any abnormality of at least Grade 1 observed within the time frame specified above will be considered treatment emergent.

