#### **7.2.2.2. Summaries of Laboratory Abnormalities**

Laboratory data that are categorical will be summarized using the number and percentage of subjects in the study with the given response at baseline and each scheduled postbaseline visit.

The following summaries (number and percentage of subjects) for treatment-emergent laboratory abnormalities will be provided by lab test and treatment group; subjects will be categorized according to the most severe postbaseline abnormality grade for a given lab test:

- Graded laboratory abnormalities (note: in addition to summarizing abnormalities throughout the study, a separate table will summarize abnormalities reported up to Day 10, collected on or prior to the B/F/TAF first dose date)
- Grade 3 or 4 laboratory abnormalities

For all summaries of laboratory abnormalities, the denominator is the number of subjects with nonmissing postbaseline values.

A by-subject listing of treatment-emergent laboratory abnormalities and treatment-emergent Grade 3 or 4 laboratory abnormalities, respectively, will be provided by subject ID number and visit in chronological order. This listing will include all test results that were collected throughout the study for the lab test of interest, with all applicable severity grades and abnormal flags displayed.

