- b Day 1 tests and procedures must be completed prior to administration of the dose of study drug
- c According to the Cockcroft Gault formula
- d Within 72 hours of permanently discontinuing study. Counsel subject regarding the importance of continuing a complete ARV therapy in accordance to standard of care, and refer patient to an appropriate HIV treatment facility.
- e Females of childbearing potential only
- f Hematology: CBC with differential and platelet count
- g Chemistries: Alkaline phosphatase, AST, ALT, GGT, total bilirubin, direct and indirect bilirubin, total protein, albumin, LDH, CPK, bicarbonate, BUN, calcium, chloride, creatinine, glucose, phosphorus, magnesium, potassium, sodium, uric acid, and amylase (reflex lipase testing if total amylase > 1.5 × ULN).
- h Fasting overnight (≥ 6 hours) required for Days 1, 3, 7, 10, 85, 169 and 225
- i FSH test is required for female subjects who have stopped menstruating for ≥ 12 months but do not have documentation of ovarian hormonal failure.
- j Vital signs blood pressure, pulse, respiration rate, and temperature, weight
- k Urinalysis and Urine Chemistry: including color & clarity, specific gravity, pH, glucose, ketones, bilirubin, urobilinogen, blood, nitrite, leukocyte esterase and microscopic (if microscopic elements are seen), urine protein, albumin, creatinine, phosphate, calcium, magnesium and uric acid
- l Part A: Serial blood samples to determine pharmacokinetics (PK) in plasma will be collected at the following time points relative to study drug dosing 0 (pre dose), 1, 2, 4, 8, 12 and 24 hours post dose.  
[REDACTED]
- n Part A: Single Anytime PK sample to be collected at the Day 3, 4, and 7 through 225 visits.
- o Part B: Plasma PK samples to be collected at the following time points relative to study drug dosing: 0 (pre dose), 0.5, 1, 2, 3, 4, 6, 8, 10, 12, 24 and 48 hours post dose; as well as at Days 4, CCI [REDACTED] 7, 8, 9 and 10 at approximately the same time in the morning as pre dose on Day 1.
- p Part B: PBMC PK samples to be collected at the following time points relative to study drug dosing: 0 (pre dose), 1, 2, 4, 6, 8, 12, 24 and 48 hours post dose, as well as at Days 4, CCI [REDACTED] 7, 8, 9 and 10 at approximately the same time in the morning as pre dose on Day 1.  
[REDACTED]

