#### 5) Graded Laboratory Abnormalities Summary

The following labels will be used for treatment-emergent laboratory abnormalities and treatment-emergent Grade 3 or 4 laboratory abnormalities summary tables and listings:

Battery	Lab Test Label Used in I-labtox Listing	Toxicity Direction	Lab Test Label Used in t-labtox Table
Hematology	Hemoglobin	Decrease	Hemoglobin (Decreased)
	Neutrophils	Decrease	Neutrophils (Decreased)
	Platelets	Decrease	Platelets (Decreased)
	WBC	Decrease	WBC (Decreased)
Chemistry	Albumin	Decrease	Albumin (Decreased)
	Alkaline Phosphatase	Increase	Alkaline Phosphatase (Increased)
	ALT	Increase	ALT (Increased)
	Amylase	Increase	Amylase (Increased)
	AST	Increase	AST (Increased)
	Bicarbonate	Decrease	Bicarbonate (Decreased)
	Corrected Calcium	Increase	Corrected Calcium (Hypercalcemia)
	Corrected Calcium	Decrease	Corrected Calcium (Hypocalcemia)
	Creatine Kinase (CK)	Increase	Creatine Kinase (Increased)
	Creatinine	Increase	Creatinine (Increased)
	GGT	Increase	GGT (Increased)

Battery	Lab Test Label Used in I-labtox Listing	Toxicity Direction	Lab Test Label Used in t-labtox Table
	Lipase	Increase	Lipase (Increased)
	Magnesium	Decrease	Magnesium (Hypomagnesemia)
	Phosphate	Decrease	Phosphate (Hypophosphatemia)
	Serum Glucose (Fasting)	Increase	Serum Glucose (Fasting, Hyperglycemia)
	Serum Glucose (Fasting)	Decrease	Serum Glucose (Fasting, Hypoglycemia)
	Serum Glucose (Nonfasting)	Increase	Serum Glucose (Nonfasting, Hyperglycemia)
	Serum Glucose (Nonfasting)	Decrease	Serum Glucose (Nonfasting, Hypoglycemia)
	Serum Potassium	Increase	Serum Potassium (Hyperkalemia)
	Serum Potassium	Decrease	Serum Potassium (Hypokalemia)
	Serum Sodium	Increase	Serum Sodium (Hypernatremia)
	Serum Sodium	Decrease	Serum Sodium (Hyponatremia)
	Total Bilirubin	Increase	Total Bilirubin (Hyperbilirubinemia)
	Urea Nitrogen (BUN)	Increase	Urea Nitrogen (Increased)
	Uric Acid	Increase	Uric Acid (Hyperuricemia)
	Uric Acid	Decrease	Uric Acid (Hypouricemia)
Urinalysis	Urine Glucose	Increase	Urine Glucose (Glycosuria)
	Urine Protein	Increase	Urine Protein (Proteinuria)
	Urine RBC (Quantitative)	Increase	Urine RBC (Hematuria, Quantitative)

- 6) PK concentration analysis visit names will follow day/hour labeling combinations defined in the protocol Section 6.6.1 (i.e. Day 1 48 hours post dose).
- 7) Clarification for “Pharmacokinetic Sampling Details and Concentrations” listings

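### Lipase, and to a lesser degree quantitative urine RBC, is measured only conditionally, so a denominator of participants with a postbaseline value gives percentages that are not incidences and cannot be compared with placebo

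*SAP*

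**What the plan says.** **When the tests are run.** Protocol section 6.6.1 puts amylase in the chemistry profile and adds that "reflex lipase testing is performed in subjects with total amylase" above 1.5 × ULN. The chemistry footnote to the SAP schedule (SAP Appendix 1) repeats the rule: "amylase (reflex lipase testing if total amylase > 1.5 × ULN". For urine, protocol section 6.6.2 includes "microscopic (if microscopic elements are seen" in the urinalysis panel. Chemistry and urinalysis are scheduled at Screening, Day 1 and most later visits.

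**How they are reported.** SAP Appendix 3, item 5, gives increased lipase its own row in the graded tables, and another to "Urine RBC (Hematuria, Quantitative". It lists no dipstick haematuria row. Section 7.2.2.2 gives number and percentage by lab test and treatment group, using each participant's worst postbaseline grade for the test. Its denominator rule is: "For all summaries of laboratory abnormalities, the denominator is the number of subjects with nonmissing postbaseline values". One table covers the whole study and a separate one covers the period up to Day 10.

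**Missing baseline.** SAP section 7.2.2.1 addresses this case: "If the relevant baseline laboratory value is missing, any abnormality of at least Grade 1 observed" is classed as treatment-emergent. Protocol section 8.6.3 has the same rule.

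Neither document has a rule for tests that are run conditionally.

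**The concern.** The denominator rule suits a test scheduled for everyone, where a missing value is incidental. For lipase, a missing value is the expected result of a normal or mildly raised amylase. Applying the rule to lipase restricts the denominator to participants selected by a post-dose laboratory abnormality.

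Graded laboratory abnormalities are a secondary endpoint (protocol sections 3.1 and 8.1.3), and safety compared with placebo is a secondary objective of Part A. With groups of 6, 8 or 10, selection of this kind can move a percentage a long way or leave no denominator at all. A reader going down a table column would take the lipase percentage to mean the same as the amylase percentage, when it answers a different question. The table up to Day 10 is the most exposed, because it has only three scheduled post-dose chemistry and urinalysis visits (Days 3, 7 and 10).

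**Working it through.** The documents give no incidence, trigger rate or denominator count for either test, so there is no stated figure to reproduce.

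**Inputs from the documents**
- Lenacapavir dose group: 6. Pooled placebo: 10. TAF cohort: 8 (SAP sections 1.2 and 1.3). All lenacapavir: 5 × 6 = 30.
- Lipase trigger: total amylase above 1.5 × ULN. In protocol Appendix 4, Grade 2 total amylase is "> 1.5 to 2.0 × ULN", so every triggered participant has amylase of Grade 2 or higher.
- Lipase Grade 1 starts above 1.0 × ULN (protocol Appendix 4).

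**Step 1: the printed percentage.** Let x be the number with a graded result, m the number tested after baseline and N the number followed, assuming everyone followed has a postbaseline amylase. The per-test figure is x/m, the figure over all followed is x/N, and their ratio is N/m.

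| Group | N | x = 1, m = 1: x/m | x = 1, m = 2: x/m | x/N |
|---|---|---|---|---|
| One lenacapavir dose | 6 | 100% | 50% | 16.7% |
| One TAF cohort | 8 | 100% | 50% | 12.5% |
| Pooled placebo | 10 | 100% | 50% | 10.0% |
| All lenacapavir | 30 | 100% | 50% | 3.3% |

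If no placebo participant triggers the reflex, the row shows 0/0 where the figure over all followed is 0/10.

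**Step 2: how often this matters.** This needs two quantities that the documents do not give, so both are assumptions: t, the probability that a participant is ever tested after baseline (5% to 50%), and q, the probability of a graded result once tested (50% or 80%). The expected per-test percentage, given that someone is tested, is q. Over all followed it is t × q. The ratio is 1/t, whatever q is. The probability of an empty denominator is (1 − t)^N.

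| t | Ratio 1/t | Nobody tested, N = 6 | Nobody tested, N = 10 |
|---|---|---|---|
| 5% | 20 | 73.5% | 59.9% |
| 10% | 10 | 53.1% | 34.9% |
| 20% | 5 | 26.2% | 10.7% |
| 30% | 3.3 | 11.8% | 2.8% |
| 50% | 2 | 1.6% | 0.1% |

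**Step 3: direction.** The distortion can also hide a difference. With q = 50%, groups with t = 10% and t = 30% both show an expected 50% per test, while the figures over all followed are 0.10 × 0.50 = 5% and 0.30 × 0.50 = 15%.

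**Step 4: the lipase numerator.** A missing lipase baseline shows only that the reflex did not fire at Screening or Day 1. Amylase at or below 1.5 × ULN does not exclude lipase above 1.0 × ULN, and no eligibility criterion limits either enzyme. Take a participant whose lipase is steady at 1.1 × ULN and whose amylase reaches 1.6 × ULN after dosing. That participant is tested for the first time, graded 1 and counted as treatment-emergent. The same gap makes x/N a lower bound, since untested participants may also have raised lipase.

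**Step 5: urine RBC.** The condition is that any microscopic element is seen, so tested participants can be Grade 0 for red cells and the selection is weaker. If microscopy was not run at baseline because nothing was seen, absence of red cells is a fair inference, and the missing-baseline rule then gives a sensible answer.

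**The case against.** The strongest reply is that little depends on these rows. SAP section 7.2 plans no formal testing of laboratory data. The tables print counts beside percentages, and 1 in a group of 6 is visible as 1 whatever the denominator. By-participant listings show all results for the test. Amylase is scheduled in every group and has its own graded row, so the pancreatic signal is not lost. The trigger is the same in every group, so the distortion favours none by design. All of this stands, and it limits the consequence to how the percentages are read.

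It can also be said that section 7.2.2.2 does not state that the nonmissing value must be for the test in question. That is true, but the table is built by lab test, so the per-test reading is the natural one. On the other reading, untested participants would count as unaffected without any note. The rule needs stating either way.

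Three stronger readings are tempting, and the documents do not support them.
- *Haematuria is reported only through the conditional test.* Section 7.2.2.2 also summarises categorical laboratory data by visit, and dipstick blood belongs to the scheduled urinalysis. Section 7.2 lists urinalysis results with flags. Only a dipstick row in the graded table is absent.
- *Most tested participants lack a baseline.* Baseline is the last value on or before dosing, with chances at Screening and Day 1, and no trigger rate is given.
- *Setting an untriggered baseline to Grade 0 would repair the numerator.* A Grade 1 or higher result after Grade 0 has risen by at least one grade, so it still counts as treatment-emergent and the numerator is unchanged.

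**Conclusion.** The point holds for lipase and, to a smaller degree, for quantitative urine RBC. On the per-test reading, the lipase percentage is conditional on a postbaseline amylase of Grade 2 or higher. It should not be read as an incidence or compared with placebo. For a single graded result among one or two tested participants, it is 100% or 50%, against 16.7% of a lenacapavir group of 6. A group with no reflex has no percentage at all.

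That arithmetic depends only on group sizes in the documents, on the per-test reading and on everyone followed having a postbaseline amylase. The frequency of such results depends on the assumed trigger rates. A reader might infer that the all-followed percentage is the true rate, or that the printed figure is biased in a known direction between groups. Neither follows: the first is a lower bound, and the second can exaggerate or mask a difference. The effect is confined to descriptive percentages; counts and listings are sound.

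**What to change.** In SAP section 7.2.2.2, state that denominators are per test, with an exception for the two conditionally run tests:
- For lipase, use participants with a nonmissing postbaseline amylase. For quantitative urine RBC, use participants with a nonmissing postbaseline urinalysis.
- Show the number actually tested beside the denominator.
- Footnote that the test is conditional, that the lipase percentage over all followed is a lower bound, and that a lipase result with no baseline test may be pre-existing.

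Optionally, add a dipstick haematuria row to the graded table in SAP Appendix 3. Dipstick blood is scheduled in every group and graded in protocol Appendix 4.

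The cost is minor SAP wording and programming, with no new data. The remaining drawback is a lipase percentage that can understate the true frequency, which the footnote makes plain.

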### **7.3. Body Weight and Vital Signs**

Descriptive statistics will be provided by treatment group for body weight and vital signs as follows:

- Baseline value
- Values at each postbaseline visit
- Change from baseline at each postbaseline visit

A baseline value will be defined as the last available value collected on or prior to the date/time of first dose of study drug. Change from baseline to a postbaseline visit will be defined as the postbaseline value minus the baseline value.

In the case of multiple values in an analysis window, data will be selected for analysis as described in Section 3.8.3. No formal statistical testing is planned.

A by-subject listing of vital signs will be provided by subject ID number and visit in chronological order. Body weight, height, and BMI will be included in the vital signs listing, if space permits. If not, they will be provided separately.

### **7.4. Prior and Concomitant Medications and Disease-Specific Medications**

Prior and concomitant medications (ie, non-antiretroviral [non-ARV] medications) collected at screening and during the study will be coded using the current version of the World Health Organization (WHO) Drug Dictionary.

Disease-specific medications (ie, nonstudy drug ARV) used prior to, during, or after the study (if collect) will be coded using the Gilead-modified WHO Drug Dictionary.

#### **7.4.1. Prior and Disease-Specific Prior Medications**

Prior and disease-specific prior medications are defined as any medications taken before a subject took the first study drug.

A summary of prior or disease-specific prior medications will not be provided.

#### **7.4.2. Concomitant Medications**

Concomitant medications are defined as medications taken on or after first dose date of study drug. Use of concomitant medications will be summarized by preferred name using the number and percentage of subjects for each treatment group. A subject reporting the same medication more than once will be counted only once when calculating the number and percentage of subjects who received that medication. The summary will be ordered by preferred term in descending overall frequency. For drugs with the same frequency, sorting will be done alphabetically.

For the purposes of analysis, any medications with a start date prior to or on the first dosing date of study drug and continued to be taken after the first dosing date, or started after the first dosing date of study drug will be considered concomitant medications. Medications started and stopped on the same day as the first dosing date of study drug will also be considered concomitant. Medications with a stop date prior to the date of first dosing date of study drug will be excluded from the concomitant medication summary. If a partial stop date is entered, any medication with the month and year (if day is missing) or year (if day and month are missing) prior to the date of first study drug administration will be excluded from the concomitant medication summary. If a partial start date is entered, any medication with the month and year (if day is missing) or year (if day and month are missing) on or after the study drug start date will be included in the concomitant medication summary. Medications with completely missing start and stop dates will be included in the concomitant medication summary, unless otherwise specified. Summaries will be based on the Safety Analysis Set. No formal statistical testing is planned.

All prior and concomitant medications (other than per-protocol study drugs) and all nonstudy drug ARV medications will be provided in by-subject listings sorted by subject ID number and administration date in chronological order.

